## 6 Statistical methods

### 6.1 Analysis populations

Safety population: all patients enrolled into the study who received at least one dose of Humira® (adalimumab)

ITT population: all randomized patients

Per-protocol (PP) population: all randomized patients who underwent AST or SOC physiotherapy for 6 months with no major protocol deviations.

### 6.2 Descriptive statistics

The number of valid and missing values, means, standard deviations, minimum, lower quartile (Q1), median, upper quartile (Q3) and maximum are reported for distributions of (quasi) continuous variables.

Absolute and relative frequencies are given for categorical variables.

### 6.3 General principles and test methods

All analyses are deliberately performed at the full level of significance of  $\alpha = 0.05$ , i.e. with no correction for multiple testing.

All treatment effects are indicated with their 95% confidence interval.

Sensitivity analyses (see section 6.4) are run with inclusion of covariates (see section 6.5) for verification of initially univariate investigated effects, in particular for the primary outcome measure.

#### (1) Primary outcome measure/endpoint

Primary assessment is based on the ITT population.

BASMI at 6 months (V5) is determined by analysis of covariance with treatment as fixed coefficient and baseline BASMI (V3) as covariate. The treatment effect is indicated with its 95% confidence interval. If the criteria for analysis of covariance are not met, suitable methods may be used (transformation of the data).

Note: BASMI (BASMIlin) is a continuous variable because it is the mean of 5 analogous assessments on a scale of 0-10.

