9.0 Research Methods

9.1 Study Design

Treatment of axSpA patients with humira® will be according to the local humira® product label and local standard of care, including timing of clinic visits, required laboratory tests and any other procedures required for appropriate therapy. Patients on humira® therapy have received the local patient information, and should be advised of the potential benefits and risks of humira® by their physicians as well as being instructed in injection techniques. Humira® will be obtained as commercially available medication. AbbVie will not provide the medication for this study.

[figure not shown]
This protocol describes a post-marketing, observational study that will exploratively investigate the impact of active supervised training compared to standard of care physiotherapy in context of humira® treatment.

Adult axSpA patients initiating treatment with humira® (adalimumab) based on current clinical practice criteria will be informed about the study. After written consent they will be enrolled in the study at the Enrollment Visit. Patients with sufficient response to humira® treatment within 12 +/- 4 weeks (as defined individually by the treating physician) and who will be eligible for active physiotherapy (according to the rheumatologist's and the physiotherapist's decision) will be randomized in an 1:1 ratio to receive either active supervised training (AST group) or standard of care physiotherapy (SOC group) (Fig.1). Randomization of the patients will be balanced regarding gender, age and disease activity (BASDAI).

Patients not eligible for FPZ training will be excluded from the study. Eligibility to participate in the study is based on the basic ability of the patient to undergo active physical exercise. The decision will be based on the physicians and the physiotherapist's discretion.

The observational period of the study will comprise a follow-up period of 12 month after Baseline Visit. An enrollment period of treatment initiation and response assessment for 3 to 5 month will precede Baseline Visit and Randomization (Fig. 1).

Figure 1: Study Design Schematic

★FPZ assessment of all patients

Study procedures will be performed as outlined in the schematic presented Table 1.

Table 1 and Table 2: Study Activities

Table 1: Study Activities	Start ADA (Enrollment Visit) V0	Response Assessment V1	FPZ Assessment V2	Randomization (Baseline Visit) V3	3 Month follow-up from baseline V4
Patient Authorization	X				

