5.0 Amendments and Updates

None

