### 1.2 External documents

Document no.	Document
1	Study Protocol "P15-710_Treat and Train_PMOS study protocol_20170220_Amendment V02_final.docx"

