#### **4.3 Study design**

The axSpA patients receive Humira® in accordance with the national Humira® label and the appropriate SOC, including as regards medical consultation schedules, requisite lab tests, and all the other procedures required for proper therapy. Patients receiving Humira® therapy have been given the German package leaflet, informed by their doctor about the benefits and risks of Humira®, and trained in the injection technique. Humira® is sourced as a commercially available medicine. AbbVie provides no medication for this study.

This SAP describes the methods of analysis used for exploratory investigation of the effects of active supervised training versus SOC physiotherapy during Humira® treatment.

Adult axSpA patients starting Humira® therapy based on the criteria employed in routine clinical practice are informed about the study. Subjects are enrolled into the study at the enrollment visit after providing their written consent. Patients who respond adequately to Humira® within  $12 \pm 4$  weeks (based on their rheumatologist's individual assessment) and are eligible for active physiotherapy (in the estimation of their rheumatologist and physiotherapist) are randomized at a ratio of 1:1. Patients are randomized to receive either active supervised training (AST group) or SOC physiotherapy (SOC group) (see Figure 1). Patients are randomized in equal proportions following stratification by age ( $\le 40$  years /  $> 40$  years), disease duration ( $< 3$  years /  $\ge 3$  years) and disease activity (BASMI  $\le 3$  /  $> 3$ ).

Patients who are not eligible for FPZ training will be excluded from the study. Eligibility for participation in the study depends on whether the patient is capable in principle of performing physical activities (ascertainment of basic trainability). The rheumatologist treating the patient and the physiotherapist make this decision.

The observational part of the study comprises a follow-up period of 12 months after the baseline visit. The baseline visit is preceded by a 3- to 5-month enrollment period during which treatment is initiated and response is assessed (see Figure 1).

[figure not shown]

Figure 1 Study design diagram

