##### 4.4.2 Secondary study endpoints

The following secondary study endpoints, which concern changes from baseline, are assessed at all visits (after 3, 6, 8 and 12 months).

- (2) Improvement in spinal mobility – BASMI
- (3) Improvement in physical functioning – BASFI NRS score (0 to 10)
- (4) Improvement in quality of life – general functioning assessed by ASAS-HI
- (5) Reduction in disease activity
  - Disease activity assessed by BASDAI
  - Percentage of study participants achieving a 50% improvement in BASDAI score (BASDAI50 response)
  - Change in disease activity from baseline assessed by ASDAS (Ankylosing Spondylitis Disease Activity Score)
  - Percentage of study participants achieving ASAS major improvement
  - Percentage of study participants achieving ASDAS clinically important improvement

- f. Percentage of study participants in ASDAS inactive disease (ASDAS < 1.3)
- g. Percentage of study participants with low disease activity (ASDAS < 2.1)
- h. Percentage of study participants with moderate disease activity (ASDAS ≥ 1.3 to < 2.1)
- i. Percentage of study participants with high disease activity (ASDAS ≥ 2.1 to < 3.5)
- j. Percentage of study participants with very high disease activity (ASDAS ≥ 3.5)
- k. Percentage of study participants achieving ASAS20
- l. Percentage of study participants achieving ASAS40
- m. Percentage of study participants achieving partial ASAS remission
- n. Change from baseline in physician's global assessment of disease activity
- o. Change from baseline in patient's global assessment of disease activity

(6) Reduction in pain

- a. Change from baseline in patient's global assessment of pain
- b. Change from baseline in patient's assessment of total back pain
- c. Change from baseline in patient's assessment of nocturnal back pain

(7) Improvement in other PROs

- a. Fatigue (BASDAI Question 1)
- b. Duration and severity of morning stiffness (mean of BASDAI Questions 5 and 6)

(8) Psychosocial risk factors – FABQ

(9) Other variables proposed for assessment:

- a. Comorbidities (screening only)
- b. Comedication:
  - i. previous and concomitant non-biologic DMARDs
  - ii. concomitant systemic glucocorticoids
  - iii. concomitant pain medication: analgesics, NSAIDs, cyclooxygenase-2 (COX-2) inhibitors

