### **4.7 *Randomization***

Subjects were randomized after stratification by the categories age ( $\leq 40$  years /  $> 40$  years), disease duration ( $< 3$  years /  $\geq 3$  years) and disease activity (BASMI  $\leq 3$  /  $> 3$ ) using SAS 9.4 statistical software (SAS Institute Inc., Cary, NY, USA). Patients are assigned to receive either active supervised training (AST group) or SOC physiotherapy (SOC group) at a ratio of 1:1 via block randomization with varying block length.

A sufficiently comprehensive randomization list was prepared and implemented in the database. Once a new patient has responded to Humira at V1, the correct stratum is selected based on the categories, and assignment is made known at V3. The use of block randomization achieves balance in the allocation of treatment within the strata regardless of occupancy.

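### Age and disease duration, which the SAP stratifies on, are named in none of its models; the protocol lists other randomisation factors, and its logistic regression is omitted without declaration

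*SAP*

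**What the plan says.** **Randomisation.** SAP 4.7: "Subjects were randomized after stratification by the categories age" (40 or younger against older), disease duration (under 3 years against 3 or more) and BASMI (3 or less against more than 3, labelled disease activity). Allocation is 1:1 in blocks of varying length. The timing is also given: "Once a new patient has responded to Humira at V1, the correct stratum is selected based on the categories"; the assignment is disclosed at V3. SAP 4.3 lists the same factors: "Patients are randomized in equal proportions following stratification by age", and so on.

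Protocol 9.1, in both supplied copies, has a different list: "Randomization of the patients will be balanced regarding gender, age and disease activity (BASDAI". It gives no cut-points.

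**Continuous endpoints.** The primary model is: "BASMI at 6 months (V5) is determined by analysis of covariance with treatment as fixed coefficient and baseline BASMI (V3) as covariate". Under SAP 6.3 (2) the secondary continuous endpoints with a baseline value are analysed in the same way. SAP 6.5 adds variables to the primary model as fixed factors, but describes them as data on response between enrollment and baseline. It names neither age, disease duration nor the strata. Protocol 9.7.6 allowed baseline data in general as well as response data.

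**Binary endpoints.** Protocol 9.7.4 plans contingency tables, chi-square and trend tests, and logistic regression for binary variables. SAP 6.3 (2) keeps the tables and tests, adds Fisher's exact test for small samples, and does not mention logistic regression. SAP 6.3 promises a 95% confidence interval for every treatment effect. SAP 4.10, on changes from planned analyses, says not applicable.

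**The concern.** Blocking within strata makes the arms more alike on the stratification factors than simple randomisation would. If those factors predict the outcome, a model without them still counts their variation as noise. The standard error is then too large for the design, the interval too wide and the test conservative.

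The two factor lists share only age, so one description of the randomisation is wrong or out of date. Until that is settled, the adjustment set cannot be written, nor the allocation reported correctly. The third label adds doubt: SAP 4.3 and 4.7 call BASMI disease activity, whereas SAP 4.4.2 puts BASMI under spinal mobility and files under disease activity "Disease activity assessed by BASDAI".

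For binary endpoints, an interval is promised but the plan does not say for what. Risk difference, risk ratio and odds ratio are all open, and the choice could be made after the data are seen.

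**Working it through.** **1. The plan's sample size.** Inputs from SAP 6.7 and the protocol's sample-size text: difference 1, SD 3.7, alpha 5% (taken as two-sided), power 80%, dropout 15%. n = 2 × (1.960 + 0.842)² × 3.7² / 1² = 214.9, so 215 per arm by normal approximation. The t-test gives 80.02% power at 216. With dropout, 216/0.85 = 254.1, rounded to 255 per arm, or 510. Both figures reproduce. The calculation uses no covariate or stratification factor.

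**2. Which factors each model contains**

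| Factor (SAP 4.7) | BASMI models | Other continuous endpoints |
|---|---|---|
| Age group | absent | absent |
| Disease-duration group | absent | absent |
| BASMI 3 or less / above 3 | carried by V3 BASMI, though the stratum is picked at V1 | absent |

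**3. Effect of the omission on the primary analysis.** Let R² be the share of residual variance, after V3 BASMI, explained by age and duration group. The documents do not give it; I assume 0 to 0.10.

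- Interval width without / with the factors = 1/√(1 − R²).
- True alpha, no attrition = 2 × [1 − Φ(1.96/√(1 − R²))].
- With 15% random dropout, about 15% of the balance is lost, so R² is replaced by 0.85 R² in the alpha formula.
- SE = 3.7 × √(1 − ρ²) × √(2/216), where ρ is the V3–V5 BASMI correlation (not in the documents). ρ = 0 treats 3.7 as the residual SD: SE = 0.356.
- Power without the factors = Φ((1/SE − 1.96)/√(1 − 0.85 R²)); with them = Φ(1/(SE√(1 − R²)) − 1.96).

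| R² | Width ratio | Alpha, no attrition | Alpha, 15% dropout | Power without → with, ρ = 0 | Gain, ρ = 0 | Gain, ρ = 0.5 |
|---|---|---|---|---|---|---|
| 0 | 1.000 | 0.050 | 0.050 | 80.2 → 80.2% | 0 | 0 |
| 0.02 | 1.010 | 0.048 | 0.048 | 80.4 → 81.0% | 0.6 points | 0.4 points |
| 0.05 | 1.026 | 0.044 | 0.045 | 80.7 → 82.2% | 1.5 points | 0.9 points |
| 0.10 | 1.054 | 0.039 | 0.041 | 81.3 → 84.2% | 2.9 points | 1.8 points |

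A simulation of the null case agrees. It used 510 randomised, 8 strata, 15% random dropout and 6,000 runs; block lengths of 2, 4 and 6 and a V1–V3 BASMI correlation of 0.9 are assumptions. At R² of 0.05 and 0.10, alpha was 0.044 and 0.042 without the factors and 0.052 and 0.052 with them (Monte Carlo error about 0.003). The standard-error ratios were 1.026 and 1.054. The mean estimate was within 0.004 of zero for both models, so there is no bias.

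**4. Binary endpoints.** SAP 4.4.2 (5) lists 11 (items b and d to m). At four follow-up visits that is 11 × 4 = 44 comparisons with no named measure. They overlap: the ASDAS categories f, h, i and j partition one score, and g is f plus h.

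In an illustration with 65/216 against 86/216 responders, chi-square gives p = 0.0341 and unadjusted logistic regression p = 0.0345, with odds ratio 1.54 (1.03 to 2.29). The test hardly changes; what is missing is the stated measure and any adjustment. With an assumed 20% against 30%, 216 per arm and Wald intervals, the same data could be reported as a risk difference of 10.0 points (1.9 to 18.1), a risk ratio of 1.50 (1.07 to 2.10) or an odds ratio of 1.71 (1.10 to 2.67).

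**The case against.** The strongest reply is that the primary model is not an error. It is the model of Protocol 9.7.3, the study describes itself as exploratory and non-confirmatory, and SAP 6.3 and 6.5 already foresee covariate-adjusted checks. This stands as far as it goes: a reader might infer that the SAP departs from the protocol's primary model, and it does not. The adjusted checks are a partial answer only, because the one sentence describing the added variables is ambiguous and names no stratification factor.

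A reader might also infer that all three factors are missing from every ANCOVA. That is not so for the primary and secondary BASMI models, which contain V3 BASMI.

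The differing factor lists may be a version matter. The SAP cites "P15-710_Treat and Train_PMOS study protocol_20170220_Amendment V02_final.docx", whereas both supplied protocol copies enter none under "5.0 Amendments and Updates". Their version pages are not available, so the supplied texts cannot show that the randomisation was run on the wrong factors. BASMI in SAP 4.3 and 4.7 could itself be a slip, since SAP 5.2 makes a similar one by assigning spinal mobility to BASDAI. If the third factor is really BASDAI, V3 BASMI does not carry it.

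Finally, the SAP does not swap one binary analysis for another: tables and chi-square tests were in the protocol already. Only logistic regression is left out. That omission, undeclared and with no effect measure named, stands.

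**Conclusion.** The point holds as a free improvement plus two reconciliations. Age and disease duration should be in the models because the SAP randomises by them, and the non-BASMI ANCOVAs should contain all the randomisation factors. The gain is modest: for R² of 0.02 to 0.10 the interval is 1 to 5% wider than it need be, alpha is about 0.048 to 0.039, and the power gain is at most about 3 points, or about 1.5 points or less at R² up to 0.05. If the factors predict nothing beyond V3 BASMI, nothing is lost. These sizes rest on the assumed R², on 216 analysed per arm, and on reading 3.7 as the residual SD; if it is a raw SD, the gain is smaller.

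A tempting stronger reading is that leaving out stratification factors biases the estimate or inflates false positives. The design gives no support for that: allocation is 1:1 within strata, and the error is on the conservative side.

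The mismatch in factors and the undeclared loss of logistic regression do not depend on R². Both need an answer before database lock.

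**What to change.** 1. **Confirm the factors.** Take factors and cut-points from the randomisation list implemented in the database. Reconcile Protocol 9.1 with SAP 4.3 and 4.7, checking against the protocol version the SAP cites, and correct the label on the BASMI factor.
2. **SAP 6.3 (1).** Specify an ANCOVA with treatment, continuous V3 BASMI, and age group and disease-duration group in the categories used at randomisation (or whatever factors the list shows). Report the protocol's model without them alongside.
3. **SAP 6.3 (2), continuous endpoints.** For endpoints other than BASMI, use treatment, the endpoint's own baseline and all randomisation factors.
4. **SAP 6.3 (2), binary endpoints.** Restore logistic regression and report the odds ratio with its 95% confidence interval. Fix one adjustment rule before database lock and apply it to every endpoint and visit, including how sparse outcomes are handled, so that adjusted and unadjusted odds ratios are not mixed by choice. Keep chi-square and Fisher tests as supportive. If logistic regression is not restored, name the effect measure for the contingency tables.
5. **SAP 4.10.** Record the added factors and, if it remains, the dropped logistic regression.

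**Cost.** A revised SAP version; version 1.0 is dated 14 February 2019, and the protocol planned data collection until Q3 2019. No new data are needed: age, sex and disease duration are collected at V0, and BASMI and BASDAI at V0, V1 and V3 (SAP 5.1). The sample size is unchanged. Each ANCOVA loses 2 to 3 degrees of freedom, out of 432 − 3 = 429 in the primary model.

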#### (2) Secondary outcome measures/endpoints

Continuous variables for which baseline data are available will be assessed in the same way as the primary outcome variable. Assessments take place at all follow-up visits (after 3, 6, 9 and 12 months).

In the absence of baseline data, the robust t-test for independent samples will be used.

Discrete outcome variables depending on treatment are assessed using contingency tables. Simple analyses for the presence of an association will be performed using a chi square test (possible Fisher's exact test in the presence of small sample sizes), and studies for associations with ordinal variables will be done using the Cochrane-Armitage test for trend.

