9.7 Data Analysis

9.7.1 Analysis populations:

Safety set: all patients enrolled and received at least one treatment with Humira®

ITT set: all patients randomized

Per protocol set (PPS): all patients randomized and performed AST or SOC physiotherapy until 6 months without severe protocol violations

Note: Several per protocol sets might be defined according coherence with AST and SOC treatment, respectively. Those specific PPS will be defined in SAP.

9.7.2 Background and demographic characteristics:

Continuously scaled variables will be described by mean, standard deviation, median, min, max, Q1 and Q3. Categorical variables will be described by counts and percentages.

9.7.3 Analysis of primary endpoint:

The primary analysis will be performed at ITT set.

The BASMI at 6 months (V5) will be analysed within an ANCOVA with treatment as fixed effect and baseline BASMI (V3) as covariate. The treatment effect will be reported with its 95%-confidence interval. In case prerequisites of ANCOVA are not given, according methods might be applied (transformation of data).

Note: The BASMI (BASMIlin) is continuously scaled, because it is the mean of 5 analog measures on a scale 0 - 10.

9.7.4 Analysis of secondary endpoints:

Continuously scaled variables with available baseline data will be analysed like the primary endpoint.

If baseline data are not available, 2-paired t-test will be applied.

The analysis of categorically scaled outcome variables by treatment will be performed by contingency tables. Related tests (χ^2 -Test, Armitage trend test) will be performed. Binary variables will be analysed by logistic regression.

All treatment related effects will be reported with their 95% confidence interval.

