#### ***4.10 Changes from planned analyses***

Not applicable.

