### **6.5 *Investigation of covariates***

Additional potential variables are included in the primary covariance model as fixed factors. This applies to baseline data describing the response to treatment between enrollment and baseline visit.

A mixed model is also implemented for the primary outcome measure in which the sites are included as random effects in order to address any patient-site dependencies.

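### The common disease-state endpoints (ASDAS <1.3, ASDAS <2.1, ASAS partial remission) are tested by unadjusted chi-square although the V3 score is collected: valid, but less precise than the data allow

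*SAP*

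**What the plan says.** SAP 6.3(2) treats the two kinds of secondary endpoint differently. For scores: "Continuous variables for which baseline data are available will be assessed in the same way as the primary outcome variable". Under 6.3(1) that means analysis of covariance with the V3 value as covariate. For discrete outcomes it gives contingency tables: "Simple analyses for the presence of an association will be performed using a chi square test", with Fisher's exact test for small samples and a trend test for ordinal variables. No covariate is named.

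SAP 4.4.2 lists the ASDAS categories as percentages: inactive (<1.3), low (<2.1), moderate (1.3 to <2.1), high (2.1 to <3.5) and very high (≥3.5). It also lists ASAS partial remission, which SAP 5.2 defines as a score below 2 in each of four domains. All are states at the visit. The schedule in SAP 5.1 collects ASDAS and the components of all four domains at V3.

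Three other places bear on the point:

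- **Protocol 9.7.4** also lists the chi-square test, but adds: "Binary variables will be analysed by logistic regression". It names no covariate. The SAP drops this sentence, while SAP 4.10, on changes from planned analyses, reads "Not applicable".
- **SAP 6.3** provides sensitivity analyses with covariates "for verification of initially univariate investigated effects, in particular for the primary outcome measure".
- **SAP 6.5**, which gives the detail, says: "Additional potential variables are included in the primary covariance model as fixed factors". That model is for BASMI.

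**The concern.** Patients are randomised only after they have responded to adalimumab, so some may already be in the target state at V3. The state at follow-up then depends partly on where the patient stood at V3. The SAP uses that information when ASDAS is analysed as a score and discards it when the same score is cut at 1.3 or 2.1.

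There are two consequences. The comparisons at 3, 6, 9 and 12 months are less precise than the collected data allow. Also, a chance difference between arms in V3 disease activity passes into the reported percentages, while the covariance analysis of the same score corrects for it. The two ASDAS results can diverge for that reason alone.

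The response endpoints (BASDAI 50, ASAS20, ASAS40, ASDAS improvement) are defined by change from baseline and are outside this point.

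**Working it through.** **1. The plan's own figure.** Inputs from SAP 6.7 and the protocol abstract: difference 1 BASMI point, SD 3.7, 80% power, 5% type I error (two-sided taken, since 95% intervals are reported).

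n = 2 × (1.960 + 0.842)² × 3.7² / 1² ≈ 215 per arm (plan: 216; power at 216 is 0.802). 216 / 0.85 = 254.1, rounded up to 255, × 2 = 510.

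The figure reproduces, and 216 per arm is used below. No power is stated for the state endpoints.

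**2. Hand check of the gain.** Take 50% vs 62% in the state (assumed).

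- Unadjusted SE = √[(0.50×0.50 + 0.62×0.38)/216] = 0.0474. z = 0.12/0.0474 = 2.53. Power ≈ Φ(2.53 − 1.96) = 0.72.
- In simulation at correlation 0.5, adjustment cut the SE of the difference to 0.92–0.93 of this. With 0.925, z = 2.74 and power ≈ Φ(0.78) = 0.78.
- For 20% vs 30%, SE = √[(0.16 + 0.21)/216] = 0.0414. z goes from 2.42 to 2.61, and power from 0.68 to 0.74.

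**3. Simulation, common states.** 216 per arm, two-sided 5%, 4,000 trials per scenario (3,000 for partial remission). Assumptions not in the documents: a normal latent score; for the ASDAS rows, SD 0.9, mean 2.0 or 2.5 and a shift of 0.3; for partial remission, domain SD 2 and inter-domain correlation 0.6. Rows 1–2 use the standardised difference, the ASDAS rows a likelihood-ratio test, and the last row adjusts for the mean V3 domain score. Entries are power (%), chi-square → V3-adjusted.

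| State (one arm vs the other) | corr. 0.3 | corr. 0.5 | corr. 0.7 |
|---|---|---|---|
| Generic, 50% vs 62% | 72→75 | 70→78 | 71→87 |
| Generic, 20% vs 30% | 69→71 | 68→74 | 66→82 |
| ASDAS <1.3, 21.8% vs 32.8% | 73→76 | 72→79 | 73→86 |
| ASDAS <2.1, 54.4% vs 67.2% | 78→81 | 79→85 | 80→92 |
| ASDAS <2.1, 32.8% vs 45.6% | 77→79 | 78→84 | 78→91 |
| Partial remission, about 16% vs 25% | 69→71 | 69→74 | 70→82 |

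The gains are about 2–3, 5–8 and 12–16 points. If the states are less common, the gains are about 1–2, 4–6 and 8–13: ASDAS <1.3 at 9.1% vs 15.9% gives 57→58, 57→62 and 57→70; partial remission at about 6% vs 11% gives 48→50, 48→52 and 49→57. At zero correlation nothing meaningful is lost (71.0% vs 71.6% in the generic model). Type I error was 4.0–6.0% for chi-square and 4.0–6.5% for the adjusted tests.

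**4. Chance V3 imbalance.** One standard error of the between-arm V3 difference is √(2/216) = 0.096 SD. In the mean-2.0 model, a 1 SD V3 difference moves the percentage below 1.3 by 10.1, 16.4 or 22.4 points at correlation 0.3, 0.5 or 0.7, and the percentage below 2.1 by 10.5, 20.2 or 27.7. Multiplying by 0.096 gives 1.0–2.2 and 1.0–2.7 points, and twice that at two standard errors. For comparison, the SE of the difference at 50% is √(2 × 0.25/216) = 4.8 points.

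**5. Rare states.** For ASDAS ≥3.5 at 4.8% vs 2.3%, the standardised difference has power 29% against 29% for chi-square at correlation 0.3, and 32% against 30% at 0.5. A likelihood-ratio test gives 31%, 31% and 38% against 29% at 0.3, 0.5 and 0.7. At 3% vs 1%, the standardised difference falls to 20–29% against 29–32% for chi-square. One reason is that the chance of no event among 216 patients at 1% is 0.99²¹⁶ = 0.11, and such a trial cannot be fitted in the ordinary way.

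**The case against.** The case for leaving the SAP alone is substantial, and most of it stands as a limit on the point.

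- **Chi-square is valid.** A reader might infer a biased or invalid test. The documents do not support that: allocation is randomised, type I error stays near 5%, and the sampling error of an unadjusted difference already allows for chance V3 imbalance. A one-standard-error imbalance is worth 1.0–2.7 points against an SE of about 4.8.
- **Little hangs on it.** The protocol calls the study non-confirmatory, the endpoints are secondary, SAP 6.3 deliberately makes no multiplicity correction, and continuous ASDAS is already adjusted for V3.
- **Not every category gains.** A reader might extend the point to all ASDAS categories. For ≥3.5, likely to be rare among drug responders, a Wald-type standardised difference gains almost nothing and can lose power. Inactive, moderate, high and very high also partition the patients, so a mixture of adjusted and raw percentages need not sum to 100.
- **Balance at randomisation.** A reader might infer that disease activity is left unbalanced by design. Protocol 9.1 names BASDAI as the disease-activity balancing factor, while SAP 4.3 and 4.7 print BASMI under that label. If BASDAI was used, it bears on one ASAS domain (items 5 and 6). Neither factor is ASDAS. The two documents need reconciling.
- **Covariate analyses.** SAP 6.3 says "in particular", not "only", for the primary outcome. But SAP 6.5 specifies covariates for the BASMI model alone, so no V3-adjusted analysis of a state is defined.
- **The protocol's logistic regression.** Restoring it would not close the gap, because it names no baseline covariate. Its undeclared omission from the SAP is a separate discrepancy.
- **V3 timing.** The SAP places the V3 assessment after randomisation, but it already accepts V3 as covariate for the primary endpoint.

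**Conclusion.** The point holds for ASDAS <1.3, ASDAS <2.1 and ASAS partial remission, as a matter of precision. The planned test is sound but ignores a baseline score that the SAP collects and uses elsewhere. The direction of the gain was the same in every common-state scenario with positive correlation. Its size rests wholly on assumed correlations, state percentages and effects: negligible if the V3-to-follow-up correlation is near zero, modest at 0.3–0.5 and material at 0.7. It does not extend to ASDAS ≥3.5 or to any state with few events. This is a low-cost improvement to exploratory secondary analyses, not an error in the plan.

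**What to change.** In SAP 6.3(2):

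1. For ASDAS <1.3, ASDAS <2.1 and ASAS partial remission, specify logistic regression with treatment and the continuous V3 score (V3 ASDAS; for partial remission, the mean of the four V3 domain scores). Report the standardised difference in percentages with its 95% CI. This keeps the estimand a difference in percentages and supplies the interval that SAP 6.3 promises for every treatment effect.
2. Keep the raw contingency table as the descriptive display, including the moderate, high and very high ASDAS categories. Label the adjusted differences separately from it.
3. For ASDAS ≥3.5, and for any state with few events in either arm, keep the SAP's chi-square or Fisher test, or use a likelihood-ratio or penalised fit, not a Wald-type standardised difference. Fix the event threshold in advance.
4. State a rule for a missing V3 score, such as imputing the overall V3 mean.

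The cost is a few lines of SAP text and SAS code before database lock, including the two small rules for sparse events and missing V3 scores. No new data or patients are needed.
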